Study Objective: To assess the impact of routine activity on the risk of preterm birth in pregnant women between 24 and 34 weeks of gestation with a sonographically diagnosed short cervix.

Primary Outcome:

- Gestational age at delivery.

Secondary Outcomes:

- Incidence of preterm contractions.
- Incidence of premature rupture of membranes (PPROM).
- Mode of delivery (cesarean section, instrumental delivery, spontaneous vaginal delivery).

Methods

Study Design This is a prospective, randomized, controlled trial comparing two groups.

Study Procedure

1. A computer-generated 1:1 randomization scheme will allocate participants to either the intervention or control group.
2. Women attending hospitalization or high-risk pregnancy clinics at Wolfson Medical Center between 24+0 and 34+6 weeks of gestation, diagnosed with a short cervix (<25 mm) via transvaginal ultrasound, will be approached by a physician and informed about the study.
3. Upon obtaining informed consent, participants will be enrolled in the study. Upon discharge, they will receive a smart band to monitor step counts. The monitoring period will last for two weeks.
4. Participant allocation will be conducted using the pre-generated randomization scheme and sealed opaque envelopes managed by an external research nurse.
5. All participants, regardless of study group assignment, will be granted medical leave from work.
6. **Control Group (Routine Activity):** Participants in this group will be instructed to continue their normal, non-strenuous routine activities without a recommendation for maximal rest.
7. **Intervention Group (Maximal Rest):** Participants in this group will be instructed to follow maximal rest guidelines, avoiding strenuous activities such as prolonged standing, carrying heavy items, or lifting children.
8. Participants will continue to receive regular follow-up in hospitalization or high-risk pregnancy clinics as per standard departmental protocols.
9. Each participant's smart band data will be linked to a dedicated email address, ensuring step count data remains blinded to researchers until study completion.
10. Step-count monitoring will cease immediately after delivery.

Eligibility Criteria

Inclusion Criteria:

- Pregnant women between 24+0 and 34+6 weeks of gestation.
- Singleton pregnancies.
- Short cervix (<25 mm) confirmed via transvaginal ultrasound.
- No medical contraindication to mobility.

Exclusion Criteria:

- Declining study participation.

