- Medical recommendation to restrict mobility (e.g., symphysiolysis, high fall risk).
- Significant maternal comorbidities.
- Fetal distress.
- Vaginal bleeding.
- PPROM.
- Medical indication for immediate preterm delivery.
- Twin or higher-order multiple pregnancies.

Withdrawal Criteria:

- Medical indication requiring preterm delivery or urgent intervention (e.g., fetal distress, maternal complications).
- Medical condition requiring strict activity limitation, contrary to group allocation.
- Participant non-compliance with study protocol, including smart band usage.

Study Variables

Primary and secondary endpoints will be assessed based on: Step count. Number of follow-up days. Gestational age at delivery. Obstetric outcomes. Demographic characteristics (BMI, age, parity, history of preterm birth). Cervical length at diagnosis.

Data Collection

Medical data, including height, weight, age, and delivery details, will be collected from the hospital's electronic medical system (Cameleon).

Step count data will be retrieved from the dedicated email address linked to each participant's smart band at the end of the monitoring period.

Statistical Methods

Sample Size: 100 participants.

Data Analysis: Data will be analyzed using SPSS. Continuous variables will be presented as median and interquartile range (IQR). Comparisons will be made using t-tests or Mann-Whitney tests for continuous variables. Categorical variables will be compared using chi-square or Fisher's exact tests. Correlations will be

analyzed using Pearson or Spearman tests. Logistic regression will be conducted to identify factors significantly associated with preterm birth.

Study Timeline Duration: Two years.

Participant follow-up: Begins at enrollment and continues until delivery.

Step count monitoring: Two-week period during pregnancy.

Ethical Considerations

The study is funded by the Department of Obstetrics and Gynecology, Edith Wolfson Medical Center.

Participants may withdraw at any time without affecting their medical care.

The study question is specific to pregnant women, and the results may help optimize management strategies for this population.

Data Privacy

Each participant will be assigned a random identification number. Personal identifiers (name, ID number, address) will be securely stored on the principal investigator's locked computer, accessible only to authorized personnel.

Informed Consent

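### Optional: the stated comparison of gestational age at delivery is unadjusted, although three baseline variables that may be prognostic are at hand; the tests are valid, and some precision may be lost

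*Protocol*

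**What the plan says.** The Primary Outcome is "Gestational age at delivery", a continuous variable. Under Statistical Methods, Data Analysis, the comparison given for continuous variables is "Comparisons will be made using t-tests or Mann-Whitney tests for continuous variables". No covariate is attached to it.

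The only multivariable model in that section has a binary dependent variable: "Logistic regression will be conducted to identify factors significantly associated with preterm birth". It lists no factors and does not say whether allocated arm is among them.

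Eligibility Criteria set the entry window: "Pregnant women between 24+0 and 34+6 weeks of gestation". Study Timeline sets the follow-up: "Participant follow-up: Begins at enrollment and continues until delivery".

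Study Variables opens with "Primary and secondary endpoints will be assessed based on: Step count. Number of follow-up days. Gestational age at delivery. Obstetric outcomes" and goes on to "Demographic characteristics (BMI, age, parity, history of preterm birth). Cervical length at diagnosis". Gestational age at entry is not in that list by name. Study Procedure describes a 1:1 computer-generated allocation and mentions no stratification. The sample size is 100.

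**The concern.** With about 50 women per arm and no stratification, the arms can differ by chance in entry gestation, cervical length or history of preterm birth. In an unadjusted comparison that difference stays in the estimate, and any outcome variance that these variables explain stays in the error term. Women enter over a window of almost 11 weeks and none can deliver before she enrols, so one of the three has a built-in link to the outcome. The trial holds this information already, and the stated comparison does not use it. At stake is some power and some width of the confidence interval.

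**Working it through.** **Inputs from the protocol.** N = 100, allocated 1:1 (50 per arm if exactly balanced); entry 24+0 to 34+6, that is 24 to 34.857 weeks; follow-up from enrollment to delivery. The 100 is given without alpha, power, SD or effect size, so there is no design calculation to reproduce.

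**Assumptions.** Two-sided alpha 0.05; a true difference of 0.566 SD, which gives the unadjusted t-test 80.0% power with 50 per arm (noncentral t); R² is the share of outcome variance that the baseline variables explain.

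**Step 1: gain or loss from adjustment.** With k covariates the variance of the arm difference is multiplied on average by f = (1 − R²) × 97/(97 − k). Effective sample size is 100/f, and the noncentrality is 0.566 × √(50/2)/√f = 2.83/√f.

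Three covariates (entry gestation, cervical length, history):

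| R² | f | Effective N | Power |
|---|---|---|---|
| 0 | 97/94 = 1.032 | 96.9 | 78.7% |
| 0.03 | 1.001 | 99.9 | 80.0% |
| 0.10 | 0.929 | 107.7 | 82.8% |
| 0.15 | 0.877 | 114.0 | 84.9% |
| 0.20 | 0.826 | 121.1 | 86.9% |

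Break-even is at 1 − R² = 94/97, so R² = 3/97 = 0.031. The cost of a covariate that explains nothing is about 1% of effective sample size.

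**Step 2: what the entry floor gives by itself.** For entry gestation alone (k = 1) break-even is R² = 1/97 = 0.010.
- If the only link is that delivery must follow entry, assumed R² of 0.002-0.014 gives 79.7-80.2% power: no change.
- Simulating the floor alone with entry uniform over the window, or weighted to later weeks, gave a correlation of about 0.04-0.05 with 15% preterm births, 0.09-0.12 with 33-34%, and 0.18-0.22 with 57-59%. Even the last lowers the standard error by at most 1 − √(1 − 0.22²), about 2.5%.
- Only if preterm risk accrues from entry (assumed R² 0.04-0.15) does entry gestation alone bring power to 81.2-85.6%.

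**Step 3: chance imbalance.** With uniform entry the SD is 10.857/√12 = 3.13 weeks, and the standard error of the arm difference in mean entry gestation is 3.13 × √(2/50) = 0.63 week. An imbalance of that size moves the unadjusted estimate by 0.2 × √R² × outcome SD. For an assumed SD of 2-4 weeks this is 0.02-0.09 week at R² 0.002-0.014 and 0.08-0.31 week at R² 0.04-0.15. The detectable difference is 0.566 × SD, or 1.1-2.3 weeks.

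**Step 4: simulated trials.** 4,000 trials per setting, 50 per arm, left-skewed outcome, 22-37% preterm, shift of 0.566 SD. The Monte Carlo error of one power figure is √(0.8 × 0.2/4000), about 0.6 points.

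| Assumed link of entry to outcome | Three-covariate R² | t-test | ANCOVA, HC2 |
|---|---|---|---|
| Floor only | 0.006 | 80.2% | 79.9% |
| Floor only | 0.025 | 79.6% | 80.0% |
| Floor only | 0.088 | 80.2% | 82.4% |
| Weekly risk from entry | 0.061 | 79.3% | 80.6% |
| Weekly risk from entry | 0.127 | 79.9% | 83.6% |
| Weekly risk from entry | 0.158 | 80.4% | 85.7% |
| Weekly risk from entry | 0.287 | 78.9% | 90.0% |

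In the three floor-only settings entry gestation explained only 0.6-0.9% of the variance, so the gain at R² 0.088 comes from the other two variables. Type I error was 4.6-5.5% for the t-test, 4.1-5.5% for Mann-Whitney and 4.6-5.2% for ANCOVA with HC2 errors. HC3 errors were slightly conservative (4.0-4.8%).

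In further simulations with an assumed weekly preterm hazard of 0.03-0.06 from entry, a covariate-adjusted rank test differed from Mann-Whitney by about −0.2 to +4 points of power, with type I error near 5%.

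**The case against.** The strongest objection is that covariate adjustment is commonly left to a statistical analysis plan, which may exist and is not shown. The protocol's list is short, does not forbid adjustment, and its statement that endpoints will be assessed on the listed variables leaves room for it. The logistic regression may also include arm, and so may be meant as an adjusted analysis. This is why the point is optional. It does not remove the point: a comparison of the continuous primary outcome is stated and takes no covariates, and a model for preterm birth is not a comparison of gestational age at delivery.

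The size also rests wholly on assumptions. That stands: the reference power, the effect, the SD, the entry distribution and every R² are assumed, and a small loss is possible.

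Three stronger readings are tempting, and none is supported.
- A reader might infer that the entry floor makes the unadjusted comparison biased or invalid. Randomisation makes the floor the same in expectation in both arms, and simulated type I error stays near 5%.
- A reader might infer that the floor itself costs much precision. Step 2 shows that it costs almost none.
- A reader might infer that a mean-based ANCOVA should replace Mann-Whitney. That depends on the form of the effect. Under a constant shift of a left-skewed outcome, Mann-Whitney had 89-99% power against 80-90% for ANCOVA. With an effect confined to births before 37 weeks it had 6-19% against about 21-84%. Keeping Mann-Whitney as a sensitivity analysis would not restore power lost in the primary test. The protocol leaves the choice between means and ranks open, and that is a separate question.

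Finally, gestational age at entry is not a listed variable. Subtracting follow-up days from gestational age at delivery recovers it only if those days are counted from enrollment; the item stands next to step count and could mean monitoring days. This is minor, since gestation must be known to establish eligibility, but it is a reason to record it outright.

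**Conclusion.** The point holds as an inexpensive, optional improvement. The protocol's tests are valid, and nothing in it is wrong or contradictory here. Adjustment changes power from an assumed 80% to about 83-87% if the three baseline variables together explain 10-20% of the variance in gestational age at delivery, leaves it unchanged at about 3%, and lowers it to 78.7% if they explain nothing. The documents do not say where in that range this population lies. The case rests on the likely prognostic value of cervical length, history and entry gestation taken together, not on the entry floor. The possible loss is about 1.3 points of power.

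**What to change.** Add to Statistical Methods, for example: *The between-arm comparison of gestational age at delivery, by allocated group, is adjusted for gestational age at entry, cervical length at diagnosis (continuous) and history of preterm birth (yes/no; nulliparous women coded no). Where a t-test would be used, the comparison is a linear model (ANCOVA) with HC2 robust standard errors; where a Mann-Whitney test would be used, it is the same model on ranks. The corresponding unadjusted test is reported alongside.*

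Add gestational age at entry to Study Variables.

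The cost is wording and one recorded item that is already known at eligibility. The statistical cost is about 1% of effective sample size per covariate that turns out not to be prognostic: for three, 100 women count as about 97. The wording leaves the choice between a mean-based and a rank-based primary test where it is; that choice should be made separately, from the form of effect expected.

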The Effect of Routine Activity on the Risk for Preterm Delivery in Women with a Short Cervix: A Randomized Controlled Trial

Principal Investigator: [name] [name]

Email: [contact]

[contact]

Co-Investigator: [name]

Institution: Department of Obstetrics and Gynecology, Edith Wolfson Medical Center

[name]

Study Protocol: 124-24-WOMC

Version: 2.0

Date: 18.12.2024

Background:

Preterm birth is defined as delivery occurring before the completion of 37 weeks of gestation (1). The incidence of preterm birth is estimated to be approximately 10% of all deliveries (2) and represents a significant cause of perinatal morbidity and mortality (3-6). Pregnant women with a shortened cervix, as determined by transvaginal ultrasound, are at an increased risk of preterm delivery (7-8). Traditionally, bed rest has been recommended for women at risk of preterm birth. Studies suggest that approximately 18% of pregnancies in the United States receive a recommendation for bed rest at some point during pregnancy (9). The rationale for bed rest has been based on the assumption that physical exertion and strenuous activity could be associated with preterm labor and that rest may reduce uterine activity (9-11). Despite the widespread use of this recommendation in obstetrics, very few prospective randomized trials have been conducted to examine its effectiveness. A recent Cochrane review on bed rest for preventing preterm birth identified only one study, which included 1,266 women (12). The study found no significant difference in preterm birth rates before 37 weeks between women assigned to full bed rest and those who did not receive any specific intervention (7.9% vs. 8.5%). Additionally, there was no evidence that bed rest reduced preterm birth rates among women with a short cervix (13). Only one study has quantitatively assessed the relationship between physical activity and preterm birth risk in women with a short cervix (14). The study evaluated 49 women with a short cervix who were instructed to wear a step-counting device for at least one week. Participants were not given specific instructions on activity limitations. The study found no benefit to reducing physical activity levels for preventing preterm birth. In fact, women with lower step counts had a higher rate of preterm birth.

Rationale for the Study: The study aims to examine the effect of routine activity in pregnant women with a short cervix on gestational age at delivery.

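### With 100 women and perhaps 10 to 40 preterm births, naming factors by significance in a logistic regression will overstate the odds ratios it reports; make the regression exploratory, small and fully reported

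*Protocol*

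**What the plan says.** Under Statistical Methods, the Protocol fixes "Sample Size: 100 participants" and closes the Data Analysis paragraph with "Logistic regression will be conducted to identify factors significantly associated with preterm birth". It does not say which covariates enter, how many, whether the model is univariable or multivariable, or what significance level applies.

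A separate section, Study Variables, lists what the endpoints will be assessed from: step count, number of follow-up days, gestational age at delivery, obstetric outcomes, "Demographic characteristics (BMI, age, parity, history of preterm birth" and cervical length at diagnosis. Allocation comes from Study Procedure: "A computer-generated 1:1 randomization scheme will allocate participants to either the intervention or control group".

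The Background defines preterm birth as delivery before 37 completed weeks. It quotes a rate of about 10% for all deliveries, and 7.9% against 8.5% in a cited bed-rest study. For the trial's own population it says only that "Pregnant women with a shortened cervix, as determined by transvaginal ultrasound, are at an increased risk of preterm delivery (7-8", with no rate.

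**The concern.** The number of preterm births, not the number of women, limits what a logistic regression can estimate. The stated purpose is to pick out factors because they are significant. When information is scarce, a factor reaches significance mostly in those samples where its estimate happens to be large, so the reported odds ratios are a biased selection. A later analysis plan can choose covariates, but it cannot add events, and the aim is already fixed in the Protocol.

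This matters because the Study Objective is the risk of preterm birth, while preterm birth is neither the primary outcome nor a listed secondary outcome. The regression is the only analysis that names it, so its odds ratios would speak most directly to the objective.

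**Working it through.** **Inputs.** From the Protocol: 100 women, and rates of 7.9%, 8.5% and about 10%, all from other populations. Assumed: a short-cervix rate of 10% to 40%, and a two-sided 5% level. The Protocol gives no inputs for its sample size, so that figure cannot be reproduced and is taken as given.

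**Candidate terms.** Study Variables offers seven possible predictors: step count, follow-up days, BMI, age, parity, history of preterm birth and cervical length. Gestational age at delivery defines the event and is not a predictor. Allocation makes eight.

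**Events per term** = 100 × rate ÷ number of terms.

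| Rate | Events | 8 terms | 4 terms |
|---|---|---|---|
| 10% | 10 | 1.25 | 2.5 |
| 20% | 20 | 2.5 | 5 |
| 30% | 30 | 3.75 | 7.5 |
| 40% | 40 | 5 | 10 |

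At the cited study's 7.9% and 8.5%, eight terms give 0.99 and 1.06.

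**Inflation after selection.** Simulation with 100 women, a true odds ratio of 1.5 per SD (log 0.405) and 2,000 trials per setting. Median odds ratio among significant results:

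| Rate | 1 term | 3 terms | 8 terms |
|---|---|---|---|
| 10% | 2.44 | 2.62 | 2.83 |
| 20% | 1.95 | 2.05 | 2.13 |
| 40% | 1.77 | 1.81 | 1.88 |

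On the log scale this runs from ln 1.77 ÷ 0.405 = 0.571 ÷ 0.405 = 1.4 times the truth to ln 2.83 ÷ 0.405 = 1.040 ÷ 0.405 = 2.6 times. Power for such a factor was only 20% to 47%. A separate simulation with four or eight terms gave 1.8 to 2.9. A stronger factor suffers less at higher rates: with eight terms and a true value of 2.0, the median significant estimate was 3.2 at 10%, 2.5 at 20% and 2.3 at 40%.

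**Bias before selection.** With four or eight terms the mean log odds ratio was 0.43 to 0.52 against 0.405. That is exp(0.43) = 1.54 to exp(0.52) = 1.68, against 1.5. A null factor shows no average bias.

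**False factors.** For eight independent null tests, 1 − 0.95^8 = 0.34, with 8 × 0.05 = 0.4 false factors expected. Simulated values were 26% to 35% (Wald, converged fits), 38% to 43% (likelihood ratio) and 29% to 33% (one factor at a time). The error per test was 4% to 5% (Wald) or 6% to 8% (likelihood ratio), so the event count has only a weak effect.

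**Failed or separated fits.** With eight terms, two of them binary and one of those present in 15% of women, the fit failed in about 24% of runs at a 10% rate, 4% at 20% and under 1% at 40%. With continuous covariates only, it almost never failed.

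**Effect of the remedy.** With four or eight terms and rates of 10% to 40%, Firth estimation brought the mean log odds ratio to 0.40 to 0.42 and removed fit failures, which had run from 1% to 29% under ordinary maximum likelihood in the same simulation.

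**The case against.** The strongest reply is that the eight-term model is an inference. Study Variables is a separate list tied to the endpoints, and nothing puts all of it into one regression. Covariates and model form are commonly left to an analysis plan, which is not shown, so their absence is no fault. This stands. It does not remove the problem, because the inflation after selection is nearly as large with one term as with eight.

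A reader might infer that the regression is bound to name chance factors because events are few. The documents do not support that. About two thirds of all-null analyses would name none, and the false-factor risk comes from testing several factors at 5%; eight valid tests would carry it with thousands of events.

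A reader might also take 1 to 5 events per term as a property of this trial. It is conditional twice over: on one model holding every listed variable, and on a rate the Protocol does not give. The 10% describes all deliveries, and the 40% is an assumption.

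Finally, the regression is supporting. The primary outcome is gestational age at delivery, compared by t-test or Mann-Whitney test, and the planned chi-square or Fisher tests could compare preterm birth between arms. This limits the consequence and also stands.

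**Conclusion.** The concern holds in a limited form. What the Protocol fixes badly is the aim: naming factors by significance with 100 women. For a moderate true effect of 1.5 per SD, the odds ratios so named would typically read about 1.8 to 2.9, whatever the number of terms. About a third of analyses with eight null factors would name at least one, as a multiplicity effect. Numerical failure is a real risk only near 10 events with a sparse binary factor.

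The size rests on an assumed preterm rate of 10% to 40%, a 5% level and independent simulated covariates. The event count could be lower still if women withdrawn for medically indicated preterm delivery are left out. The primary comparison is not affected.

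**What to change.** Replace the stated aim of identifying significant factors with a logistic regression labelled exploratory, and specify that:

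- A few covariates are fixed in advance, including allocation, and the others are known at entry. Number of follow-up days should not be among them: the Study Timeline runs follow-up until delivery, so it may partly encode the outcome. Step count is also measured after allocation and can be reported descriptively. Which baseline covariates to keep is the investigators' choice.
- The model is fitted by Firth penalised likelihood. Even four terms leave only 2.5 to 10 events each, so penalisation is still warranted.
- Every odds ratio is reported with its 95% CI, significant or not, with no selection by p-value. Firth estimation deals with small-sample bias and failed fits; full reporting is what removes the selection inflation.

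The cost is a change of wording and software: Firth estimation needs an SPSS extension or free software. Fewer factors can be claimed. No new data and no change to patient care are needed.
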